10.4. Criteria for Potentially Clinically Significant Values (PCSV)

Parameter	PCSV
Clinical chemistry	
ALT	By distribution analysis: >2 ULN and baseline \leq 2 ULN >3 ULN and baseline \leq 3 ULN >5 ULN and baseline \leq 5 ULN >10 ULN and baseline \leq 10 ULN >20 ULN and baseline \leq 20 ULN
AST	By distribution analysis: >2 ULN and baseline \leq 2 ULN >3 ULN and baseline \leq 3 ULN >5 ULN and baseline \leq 5 ULN >10 ULN and baseline \leq 10 ULN >20 ULN and baseline \leq 20 ULN
Alkaline Phosphatase	> 1.5 ULN and baseline \leq 1.5 ULN
Total Bilirubin	> 1.5 ULN and baseline \leq 1.5 ULN > 2 ULN and baseline \leq 2 ULN
Conjugated bilirubin	> 35% total bilirubin (when total bilirubin >1.5 ULN)
ALT and Total Bilirubin	ALT > 3 ULN and Total Bilirubin > 2 ULN and baseline ALT \leq 3 ULN or Total bilirubin \leq 2 ULN
CPK	> 3 ULN and \leq 5 ULN and baseline \leq 3ULN >5 ULN and \leq 10 ULN and baseline \leq 5 ULN >10 ULN and baseline \leq 10 ULN
Creatinine	\geq 150 μ mol/L (adults) \geq 30% from baseline \geq 100% from baseline
CLcr (mL/min) (Estimated creatinine clearance based on the Cockcroft-Gault equation)	\geq 15 - <30 (severe decrease in GFR) \geq 30 - < 60 (moderate decrease in GFR) \geq 60 - <90 (mild decrease in GFR) \geq 90 (normal GFR)
eGFR (mL/min/1.73m ²) (Estimate of GFR based on an MDRD equation)	\geq 15 - <30 (severe decrease in GFR) \geq 30 - < 60 (moderate decrease in GFR) \geq 60 - <90 (mild decrease in GFR) \geq 90 (normal GFR)

Parameter	PCSV
Uric Acid Hyperuricemia: Hypouricemia:	>408 $\mu\text{mol/L}$ <120 $\mu\text{mol/L}$
Blood Urea Nitrogen	≥ 17 mmol/L
Chloride	<80 mmol/L >115 mmol/L
Sodium	≤ 129 mmol/L ≥ 160 mmol/L
Potassium	< 3 mmol/L ≥ 5.5 mmol/L
Glucose Hypoglycaemia Hyperglycaemia	≤ 3.9 mmol/L and < LLN ≥ 7 mmol/L (fasted); ≥ 11.1 mmol/L (unfasted)
HbA1c	>8%
Albumin	≤ 25 g/L
CRP	> 2 ULN or >10 mg/L, if ULN not provided
Hematology	
WBC	< 3.0 Giga/L (3000/ mm^3) (Non-Black) < 2.0 Giga/L (2000/ mm^3) (Black) ≥ 16.0 Giga/L (16000/ mm^3)
Lymphocytes	>4.0 Giga/L
Neutrophils	< 1.5 Giga/L (1500/ mm^3) (Non-Black) < 1.0 Giga/L (1000/ mm^3) (Black)
Monocytes	>0.7 Giga/L
Eosinophils	> 0.5 Giga/L (500/ mm^3) or > ULN if ULN ≥ 0.5 Giga/L
Hemoglobin	≤ 115 g/L (Male); ≤ 95 g/L (Female) ≥ 185 g/L (Male); ≥ 165 g/L (Female) Decrease from Baseline ≥ 15 g/L Decrease from Baseline ≥ 20 g/L
Hematocrit	≤ 0.37 v/v (Male) ; ≤ 0.32 v/v (Female) ≥ 0.55 v/v (Male) ; ≥ 0.5 v/v (Female)
RBC	≥ 6 Tera/L

Parameter	PCSV
Platelets	< 100 Giga/L (100 000/mm ³) ≥700 Giga/L (700000/mm ³)
Urinalysis	
pH	≤4.6 ≥8
Vital signs	
HR	≤ 50 bpm and decrease from baseline ≥ 20 bpm ≥ 120 bpm and increase from baseline ≥ 20 bpm
SBP	≤ 95 mmHg and decrease from baseline ≥ 20 mmHg ≥ 160 mmHg and increase from baseline ≥ 20 mmHg
DBP	Young and elderly patients ≤ 45 mmHg and decrease from baseline ≥ 10 mmHg ≥ 110 mmHg and increase from baseline ≥ 10 mmHg
Orthostatic Hypotension	SBP St – Su ≤ - 20 mmHg DBP St – Su ≤ - 10 mmHg
Weight	≥5% increase versus baseline ≥5% decrease versus baseline
ECG parameters	
HR	≤ 50 bpm and decrease from baseline ≥ 20 bpm ≥ 120 bpm and increase from baseline ≥ 20 bpm
PR	≥220 ms and increase from baseline ≥20 ms
QRS	≥ 120 ms
QTc Borderline Prolonged* Additional	Absolute values (ms) Borderline 431-450 ms (Male) 451-470 ms (Female) Prolonged* > 450 ms (Male) > 470 ms (Female) QTc ≥500 ms Increase versus baseline (Males and Females) Borderline Δ 30-60 ms Prolonged * Δ > 60 ms

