7.2.1. Inclusion Criteria

A patient must meet the following criteria to be eligible for inclusion in the study:

1. Males and females ages 5 to 11 years at the time of the screening visit
2. Diagnosis of functional HoFH by either genetic or clinical criteria:

Genetic Criteria

- a. Documented functional mutation or mutations in both LDLR alleles
Note: Patients who have null receptor mutations on both LDLR alleles, ie, double null, are eligible
- b. Documented homozygous mutations in LDLRAP1, or homozygous or compound heterozygous mutations in APOB or PCSK9
Note: Patients who are double heterozygous, i.e. mutations on different genes [LDLR/PCSK9 or LDLR/APOB] are eligible

Clinical Criteria

- c. Untreated TC >500 mg/dL (>13 mmol/L) and triglycerides (TGs) <300 mg/dL (<7.8 mmol/L)

AND

Both parents with documented TC >250 mg/dL OR cutaneous or tendinous xanthoma in the study patient before age 10 years

3. LDL-C >130 mg/dL at the screening visit
4. Body weight \geq 15 kg
5. Receiving stable maximally tolerated therapy*at the screening visit

*Maximally tolerated therapy could include a daily statin.

Note: Patients who are not able to be on a maximum daily statin should be on the appropriate dose for the patient or no statin, according to the investigator's judgment. Some examples of acceptable reasons for a patient taking a lower statin dose include but are not limited to: adverse effects on higher doses, lack of efficacy, regional practices, local prescribing information, concomitant medications. The reason(s) will be documented in the case report form (CRF).

6. Willing and able to comply with clinic visits and study-related procedures
7. Parent(s) or legal guardian(s) must provide the signed informed consent form (ICF). Patients \geq 5 years of age (or above age determined by the IRB/EC and in accordance with the local regulations and requirements) must also provide informed assent forms (IAFs) to enroll in the study, and sign and date a separate IAF or ICF signed by the parent(s)/legal guardian(s) (as appropriate based on local regulations and requirements)

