4.8.3. Vital Signs

Vital signs parameters will include weight (kg or lb), height (cm or in), BMI (kg/m²), heart rate (bpm), respiration (rpm), temperature (C or F), systolic and diastolic blood pressure (mmHg) after resting at least five minutes. Both actual test values and “change from baseline” values (defined as the post-baseline value minus the baseline value) will be used in the result summaries. Potentially clinically significant values (PCSV) ranges will be applied to the vital sign parameter values as applicable (see [Appendix 10.4](#) for PCSV definitions).

BMI and height percentiles will be calculated (Cole, 1992; WHO, 2006; Rigby, 2004).

4.8.4. 12-Lead Electrocardiography (ECG)

A standard 12-lead ECG will be performed at specified time points according to [Appendix 10.7](#). The ventricular rate, PR, QRS, RR, QTcF, QTcB, and QT intervals will be recorded. Electrocardiogram assessments will be described as normal or abnormal.

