5.8. Analysis of Safety Data

In general, for main study part (Part A or Part B), the summary of safety results for patients in the safety analysis set will be presented by each study part. No formal inferential testing will be performed. Summaries will be descriptive in nature.

For Part C, the summary of safety results for patients in the Part C safety analysis set will be presented for all patients and by main study part (Part A or Part B) in which patients are originally enrolled at the beginning of the study.

In addition, the safety analyses will be performed on the pooled data in the pooled safety analysis set. The summary of safety results will be presented by patient groups defined in Section 2.4.1.

General common rules

All safety analyses will be performed, unless otherwise specified, using the following common rules:

- Safety data in patients who do not belong to the safety analysis set (i.e., exposed but not enrolled) will be listed separately.
- PCSV values are defined as abnormal values considered medically important by the Sponsor according to predefined criteria/thresholds based on literature review and defined by the Sponsor for clinical laboratory tests and vital signs (PCSV version dated January 2009 [[Appendix 10.4](#)]). Considering that the threshold defined in the PCSV list for monocytes and basophils can be below the ULN, the following PCSV criterion will be used for the PCSV analysis of monocytes and basophils:
 - PCSV criterion for monocytes: >0.7 Giga/L or $>ULN$ (if $ULN \geq 0.7$ Giga/L).
 - PCSV criterion for basophils: >0.1 Giga/L or $>ULN$ (if $ULN \geq 0.1$ Giga/L).

- PCSV criteria will determine which patients had at least 1 PCSV during the respective TEAE periods, taking into account all evaluations including unscheduled or repeated evaluations.
- The treatment-emergent PCSV denominator for a given parameter will be based on the number of patients assessed for that given parameter at least once during the respective TEAE periods.
- All measurements, scheduled or unscheduled, fasting or not fasting, will be assigned to Global Analysis Windows defined in [Appendix 10.2](#) in order to provide an assessment for the screening visit through follow-up visit time points.
- For quantitative safety parameters including central laboratory measurements and vital sign scores, descriptive statistics will be used to summarize observed values and change from baseline values by visit.

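### The SAP's blood-pressure PCSV limits have no age reference, so in children aged 5-11 the high flag is almost out of reach while the low systolic flag is just a 20 mmHg fall

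*SAP*

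**What the plan says.** Eligibility (Protocol 7.2.1) is "Males and females ages 5 to 11 years at the time of the screening visit".

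SAP 10.4 gives one set of blood-pressure limits for everyone, each joining a level to a change from baseline:

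- High systolic: at least "160 mmHg and increase from baseline" of 20 mmHg or more.
- Low systolic: at most "95 mmHg and decrease from baseline ≥ 20 mmHg".
- High diastolic: 110 mmHg or more with a rise of 10 or more.
- Low diastolic: at most "45 mmHg and decrease from baseline ≥ 10 mmHg".

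The only age wording in these rows is the diastolic label, "Young and elderly patients". SAP 5.8 identifies the list as a sponsor version dated January 2009. Its creatinine row is marked as applying to adults. Elsewhere the SAP does use growth references: in 4.8.3, "BMI and height percentiles will be calculated". It does nothing similar for blood pressure.

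A child counts as flagged if one post-baseline reading in the TEAE period meets a criterion (SAP 5.8.4), "taking into account all evaluations including unscheduled or repeated evaluations" (SAP 5.8). Dosing-day blood pressure is taken before the dose and 30 and 60 minutes after the infusion ends (Protocol 9.2.3.1).

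**The concern.** The PCSV table is the only categorical analysis of blood pressure. If its upper limits lie far above the pressures of these children, an empty high column says little about whether pressure rose. If its lower limits exclude little, the low column mixes ordinary variation between readings with real falls.

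The table also has a job that no other numeric summary does. Under SAP 6.4, when several values fall on one day the first is used, so on dosing days the by-visit summaries take the pre-dose value. In addition, the quantitative period in SAP 5.8.3 starts the day after the first dose. The post-infusion readings therefore reach a specified numeric summary only through PCSV, and those limits were not set with reference to age.

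**Working it through.** The plan states no expected flag rate and no paediatric reference values, so there is no figure of its own to reproduce.

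**Step 1: arithmetic on the rules, with no outside input.** For baseline b, the required changes are:

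- high systolic: max(20, 160 − b); low systolic: max(20, b − 95)
- high diastolic: max(10, 110 − b); low diastolic: max(10, b − 45)

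| Baseline (mmHg) | Rise for high flag | Fall for low flag |
|---|---|---|
| Systolic 90 | 70 | 20 |
| Systolic 100 | 60 | 20 |
| Systolic 110 | 50 | 20 |
| Systolic 115 | 45 | 20 |
| Systolic 130 | 30 | 35 |
| Diastolic 55 | 55 | 10 |
| Diastolic 60 | 50 | 15 |
| Diastolic 65 | 45 | 20 |

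Since 115 − 20 = 95, the 95 mmHg level adds nothing at any baseline of 115 or less. Since 160 − 20 = 140, the 160 mmHg level governs the high flag at any baseline below 140.

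**Step 2: number of readings.** Vital signs in Part B are due at 9 visits after baseline. Six dosing days add 2 post-infusion readings each: 9 + 6 × 2 = 21 post-baseline readings per child.

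**Step 3: simulation with assumed values.** None of the following is in the documents: mean pressure 95/58, 100/60 or 108/64 mmHg; between-child SD 8 (systolic) and 6 (diastolic); within-child SD 5, 7 or 9; independent readings; one baseline reading. There were 200,000 children per scenario, with the rules applied as written.

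Percentage of children with at least one low flag when pressure does not truly change:

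| Mean | Within-child SD | Systolic | Diastolic | Either |
|---|---|---|---|---|
| 95/58 | 5 | 2.9 | 15.8 | 18.3 |
| 95/58 | 7 | 18.7 | 36.6 | 48.4 |
| 95/58 | 9 | 37.3 | 55.5 | 72.1 |
| 100/60 | 5 | 2.5 | 11.1 | 13.4 |
| 100/60 | 7 | 17.3 | 29.4 | 41.6 |
| 100/60 | 9 | 35.9 | 48.2 | 66.8 |
| 108/64 | 5 | 1.6 | 4.5 | 6.0 |
| 108/64 | 7 | 12.1 | 15.8 | 26.0 |
| 108/64 | 9 | 28.4 | 32.4 | 51.6 |

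The middle scenario corresponds to 0.416 × 14 = 5.8 of the 14 children planned for Part B. In the same nine scenarios a high systolic or diastolic flag occurs in at most 0.04% of children.

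**Step 4: a true systolic rise.** With mean 102, between-child SD 8, within-child SD 7 and 21 readings, a sustained rise flags the following shares as high:

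| True rise (mmHg) | Children flagged high |
|---|---|
| 20 | 0.3% |
| 30 | 4.8% |
| 40 | 29% |

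**The case against.** The strongest reply is that PCSV is one descriptive display among several. SAP 5.8.4 also summarises values and changes from baseline by visit, and a sustained rise of 20-40 mmHg would show there. Investigators judge the clinical significance of vital signs and report adverse events (Protocol 10.1.1). Infusion reactions must be reported as AEs, and moderate or severe ones are AESIs (Protocol 8.5.1 and 10.1.4). SAP 5.8.2 tabulates them by intensity, per administration and by time to first reaction. All of this stands. A reader might infer that the trial could not show drug-related hypertension, or that a true infusion-related fall would be hidden. The documents do not support either inference.

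It is also tempting to say that the low flag fires on normal variation. Every low flag also needs a fall of 20 mmHg systolic or 10 mmHg diastolic. Whether noise alone produces such falls depends on the within-child SD, which is not given; at SD 5 the systolic flag affects only about 2% to 3% of children. The combined figure is driven more by diastolic pressure (29% against 17% at 100/60, SD 7). There the 45 mmHg level does screen: from a baseline of 60 it demands a 15 mmHg fall. Allowing same-day readings to correlate at 0.5 to 0.7 lowers the 41.6% to roughly 38% to 35%.

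The PR, QRS and heart-rate limits also lack an age term, but the documents give no basis for showing a consequence. ECGs are separately classed as normal or abnormal, and the QTc row includes change limits that do not depend on age. Finally, the blood-pressure rows are not themselves labelled adult. That is an inference from the generic list and its creatinine row.

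**Conclusion.** The point holds for systolic and diastolic pressure. The lack of any age reference, and the gap between a 20 mmHg fall and a rise of at least 45 mmHg at baselines of 115 or less, follow from the SAP alone. That the high flag is almost out of reach holds in every assumed scenario. The low-flag count may be largely noise: about 6% to 72% of children for either pressure, and about 2% to 37% for systolic alone, across within-child SDs of 5 to 9. That part is a range under assumptions and not a finding of fact.

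The practical loss is limited, because these are descriptive tables without testing and other safety displays remain. It is greatest for the 30- and 60-minute post-infusion readings. The change should be made, but neither the primary endpoint nor patient protection rests on it.

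**What to change.** In SAP 10.4, replace the fixed systolic and diastolic levels with upper and lower percentiles for age, sex and height from a named paediatric reference, and keep the existing change-from-baseline conditions. Age, sex and height are already collected. For PR, QRS and heart rate, add a sentence stating whether the listed limits are considered suitable at ages 5-11, and why. These are flags for analysis only; no treatment rule changes.

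The cost is SAP text and one programmed lookup table. Blood-pressure PCSV counts would no longer be directly comparable with those of the adult studies. Tabulating the current criteria alongside the new ones would meet that.

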2.4. Combining Data Across Study Parts

This section describes the integrated data pool and the data pooling strategy for analysis. By combining the individual data across study parts into an integrated data pool, there is a better chance for detecting a safety signal, for example, in uncommon adverse events (AEs), and a more accurate estimation of the rate for common AEs.

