2.4.1. Data Pooling Strategy for Statistical Analyses

All post-baseline visit data from Part B and Part C will be included in the pool. Data in Part A will not be integrated into the data pool, since the safety profile for the single treatment administration in Part A can be different from the multiple study treatment administrations in Parts B and C. Patients enrolled in Part A will only contribute Part C data to the pool.

The following safety and efficacy parameters will be included in the pooled datasets: selected demographics and baseline characteristics, evinacumab exposure, AEs (including all TEAEs, SAEs, TEAE leading to permanent treatment discontinuation, death, AESIs), laboratory data, vital signs, ECGs, and lipid parameters (calculated LDL-C, Apo B, non-HDL-C, TC, Lp(a)).

The integration of evinacumab data includes study treatment period and follow-up data collected during Part B and Part C. Patients participating in multiple Parts of the study will have their individual data (within a patient) chronologically combined across those parts as follows:

- A. Patients treated in Part A who proceed to be treated in Part C: Common reference point for pooled study treatment Day 1 is Part C Study Day 1. Note: Part A data will not be included in the pool.
- B. Patients treated in Part B: A Part B patient will have the Part B assessments combined with Part C, if applicable, to assess longer term evinacumab exposure. Specifically, Part C visits will be chronologically appended to the last Part B visit, so all patients in Part B will have a common reference for first study treatment, defined as Part B first study treatment (Study Day 1). Operationally, Extension Study Day will be defined for Part C visits as Part C visit date – Part B first study treatment date +1.

Using the redefined Study Day structure above, individual patient data will be pooled. Specifically, patients in Bullet A + Bullet B above will be pooled, using the structure of redefined Study Day definitions (common reference for first study treatment) also described above for evinacumab treatment duration. A pooled analysis visit window label will be defined using the evinacumab treatment duration (see [Appendix 10.2](#)). Following the overlay of the pooled data visit windows to each patient's data, the data are pooled by visit, as well as assessment date, for repeated study assessments (example: laboratory assessments).

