4.8. Safety Variables

Patient safety will be assessed through the collection of reported adverse events (AEs), clinical laboratory data, vital signs, Tanner stages and ECG. Unless otherwise noted, the baseline value is defined as the last available value before the first dose of study treatment, regardless of the study treatment period.

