4.8.1. Adverse Events Variables

The period of safety observation starts from the time when the patient gives informed consent and continues into the following periods:

- The PRE-TREATMENT period is defined from the day the ICF is signed to the day before the first dose of study treatment administration.
- The treatment-emergent adverse event (TEAE) period (Part A or Part B) is defined from the day of the first dose of study treatment administration to the day of the last dose of study treatment administration in Part A or Part B respectively + 168 days (24 weeks). For patients entering Part C, the TEAE period is truncated at the day before the first study treatment administration in Part C.
- The Part C TEAE period is defined from the day of the first study treatment administration in Part C to the day of the last study treatment administration in Part C + 168 days (24 weeks).
- The pooled TEAE period is defined below:
 - Part A Patients: defined as the Part C TEAE period.
 - Part B Patients: defined from the day of the first study treatment administration in Part B to the day of the last study treatment administration in Part C + 168 days (24 weeks) or to the last study treatment administration in Part B + 168 days (24 weeks) for patients not entering into Part C.
- The POST-TREATMENT period is defined from the day after the end of the respective TEAE periods to the last study visit.

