5. STATISTICAL METHODS

In general, patient data collected in Part A will be summarized for all patients (i.e., Part A Total). For Part B, data will be summarized again for all patients (i.e., Part B Total). Part C data summaries will show three columns, specifically, patients treated in Part A, patients treated in Part B, and Total. The baseline value is defined as the last available measurement prior to the date of the first study treatment administration regardless of the study treatment period.

In addition, pooled analyses will summarize data in three columns, specifically, Part A Patients, Part B Patients, and Total. The baseline value for the pooled analyses is defined as the last available measurement prior to the date of the first study treatment administration regardless of the study treatment period. Note: Although Part A patients only contributed data from Part C for the pooled analyses, Part A patient's baseline is defined as Part A baseline for variable derivations.

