5.8.4. Analysis of Vital Signs

For respective treatment period as defined for clinical laboratory measurements (Section 4.8.2), the vital sign actual values and change from baseline values obtained while sitting will be descriptively summarized at baseline and each post-baseline visit by at least patient number, mean, median, Q1, Q3, SD, minimum and maximum. Mean changes from baseline, with the corresponding SE, can be plotted at each visit in the case results warrant further investigation.

Individual patient vital sign measurements (regardless of sitting position) will be additionally evaluated by PCSV criteria, specifically identifying patients with at least one post-baseline measurement that meets the PCSV criteria within the TEAE period. The incidence of PCSVs at any time during the respective TEAE periods will be summarized regardless of the baseline level, and again according to the following baseline categories:

- Normal (according to PCSV criterion/criteria)/missing
- Abnormal according to PCSV criterion or criteria

Patient listings of vital sign measurements that meet PCSV criteria will be provided for the report appendix.

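### The ≥5% weight-increase flag in SAP 10.4 is not adjusted for growth, so in the Part C and pooled tables its count mixes normal growth with any drug effect

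*SAP*

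**What the plan says.** - **Criterion.** The weight row of SAP 10.4 has two lines, "≥5% increase versus baseline" and the matching 5% decrease. Neither depends on age, height or time since baseline. SAP 5.8 identifies the source as the sponsor's list ("PCSV version dated January 2009") and states adaptations only for monocytes and basophils.
- **Counting rule.** SAP 4.8.3 treats weight as a vital sign subject to PCSV ranges. SAP 5.8.4 counts children by "identifying patients with at least one post-baseline measurement that meets the PCSV criteria within the TEAE period", so one value is enough.
- **Baseline.** Under SAP 4.8, "the baseline value is defined as the last available value before the first dose of study treatment, regardless of the study treatment period". SAP 5 adds that for Part A patients in the pool "baseline is defined as Part A baseline for variable derivations", although only their Part C data are pooled.
- **Tables.** SAP 5.8 tabulates safety for Part A, Part B, Part C and the pool. SAP 2.4.1 puts "laboratory data, vital signs, ECGs, and lipid parameters" in the pool, and SAP 2.4 justifies pooling on the ground that "there is a better chance for detecting a safety signal".
- **Growth-referenced measures.** SAP 4.1 defines BMI categories by percentile at baseline, and SAP 4.8.3 calculates BMI and height percentiles. Neither is tied to the weight flag, and no table of percentile change is named.

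**The concern.** A fixed percentage change in weight is a workable screen over a short interval. In growing children its meaning changes as the interval lengthens, because ordinary growth alone will eventually cross the line. Here the interval is longest in the Part C and pooled tables, which describe long-term safety. Protocol 3.2.1 says the study length was chosen partly to assess growth and development. Every patient receives evinacumab, so no control group is available from which to subtract expected growth. A high count could be read as a weight signal when it is growth, or a real excess could be lost in a count that is already near its ceiling.

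**Working it through.** **1. Elapsed time.** The protocol's own totals reproduce: 8 + 2 + 16 + 48 + 24 = 98 weeks (Parts A and C) and 8 + 2 + 24 + 48 + 24 = 106 weeks (Parts B and C). From first dose to Part C week 48 is 16 + 48 = 64 weeks or 24 + 48 = 72 weeks. SAP Table 5 agrees: pooled week 72 is day 505 = 72 × 7 + 1 from Part B day 1.

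**2. Growth rate that trips the flag.** Rate = 0.05 × baseline weight ÷ (weeks ÷ 52). The 25 kg example is the protocol's own weight cut for Part A; 5% of it is 1.25 kg.

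| Time since baseline | Rate at 25 kg (kg/year) |
|---|---|
| Part A week 16 | 4.06 |
| Part B week 24 | 2.71 |
| 64 weeks (Part A entrant, Part C week 48) | 1.02 |
| 72 weeks (Part B entrant, Part C week 48) | 0.90 |

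A 45 kg child at 72 weeks needs 2.25 ÷ (72/52) = 1.62 kg/year.

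**3. Follow-up to end of study.** The Part C TEAE period runs to 168 days after the last Part C dose, and weight is taken at EOS. Protocol Table 3 shows a dose at week 48, which puts EOS at 64 + 24 = 88 or 72 + 24 = 96 weeks and the 25 kg threshold at 0.74 or 0.68 kg/year. SAP Table 4 targets the last follow-up visit for completers at day 477 = 68 × 7 + 1, that is Part C week 68, which implies a last dose at week 44. EOS is then at 84 or 92 weeks and the threshold is 0.77 or 0.71. Either way it is about 0.7–0.8 kg/year, but the passages must be reconciled. Children entering a CUP or EAP may skip this visit.

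**4. Share flagged by growth alone (simulation; growth rates are assumptions).** Baseline weight is normal with mean 27 and SD 7 kg truncated at 15 kg, or uniform 15–45 kg. Growth SD is 0.75 or 1.0 kg/year, and weighing error is 0 or 1%. A child is flagged if any scheduled weight is at least 5% above baseline. Ranges are the minimum and maximum over these scenarios.

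| Mean growth (kg/year) | By Part C week 48 | Part B to week 24 | Part A to week 16 |
|---|---|---|---|
| 1.0 | 40–59% | 2–11% | 0–4% |
| 1.5 | 60–80% | 7–19% | 1–7% |
| 2.0 | 77–92% | 16–30% | 2–11% |
| 3.0 | 95–100% | 43–58% | 12–26% |

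**5. Can the count still show a drug effect?** Pooled count = 6 × share (Part A entrants) + 14 × share (Part B patients), assuming all 20 planned children enter Part C. The added children for an assumed drug-related 1 kg/year are:

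| Mean growth (kg/year) | Added, of 20 |
|---|---|
| 1.0 | 6–8 |
| 1.5 | 4–6 |
| 2.0 | 2–3 (from 16–18 to 19–20) |
| 2.5 | 0.5–2 |

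In the Part B table (14 children), at 2.0 kg/year, the same excess moves the count from 2–4 to 6–8, which is 3–5 more.

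**6. The decrease flag.** Growth since the old baseline works against it. A 25 kg child growing 2 kg/year weighs 25 + 2 × 72/52 = 27.8 kg at 72 weeks. To reach 23.75 kg (5% below baseline) that child must lose 4.0 kg, or 14.5% of current weight.

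**The case against.** The strongest reply is that this is one over-inclusive row in a descriptive screen. No decision, dose choice or stopping rule depends on it. Weight, height and BMI are summarised by visit, BMI and height percentiles are calculated, Tanner stage is tabulated, and a reader of a trial in this age group expects weight gain. The SAP's signal-detection argument for pooling gives uncommon adverse events as its example, not weight. All of this stands and limits the importance of the point. It does not remove it, because the plan links none of these measures to the flag.

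A second reply is that the size depends on growth rates the documents do not give. That also stands. A reader might infer that the flag is useless, or that nearly every child will be flagged. The documents do not support that: heavier children need faster growth, a 25 kg Part A entrant gaining exactly 1.00 kg/year reaches only 4.9% at week 64, and the count still discriminates if growth is slow.

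A reader might also infer that the flag should be deleted in favour of percentiles. Nothing shown here establishes that BMI categories in about 20 children, at a few height visits, would detect the same excess better. Presenting them alongside is enough.

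**Conclusion.** The point holds for the Part C and pooled tables. The 5% weight-increase criterion is carried over without adjustment for growth, against a baseline 64 or 72 weeks old at Part C week 48. A 25 kg child therefore trips it at about 1.0 or 0.9 kg/year. The thresholds, elapsed times and baseline rule come from the documents and arithmetic. The shares flagged and the loss of discrimination rest on assumed growth and baseline-weight distributions. Under those, discrimination is poor mainly at mean growth of about 2 kg/year and above, and reasonable near 1 kg/year.

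A reader might extend the criticism to the Part A and Part B tables. The short intervals there keep the threshold at 4.1 and 2.7 kg/year for a 25 kg child, so the flag remains usable. Efficacy and dose selection are untouched. This is a worthwhile, inexpensive improvement to descriptive safety reporting, not a threat to the study's conclusions.

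**What to change.** In the Part C and pooled tables:

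- Keep the weight-increase flag. Next to it, present change in BMI-for-age and height-for-age percentile, and a shift table over the BMI categories of SAP 4.1 (<P5, P5 to <P85, P85 to <P95, ≥P95).
- Do this at each visit with a height measurement: Part C weeks 24, 48 and EOS. For Part B patients, Part C weeks 24 and 48 fall at pooled weeks 24 + 24 = 48 and 24 + 48 = 72.
- Add a footnote that the weight-increase count is not growth-adjusted and should not be read alone as a drug signal, and that growth since the old baseline makes the 5% decrease flag less sensitive.

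Leave the Part A and Part B tables unchanged. Separately, reconcile protocol Table 3 with SAP Table 4 on the timing of the last Part C dose, since it fixes the EOS week.

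The cost is a SAP edit and a small amount of programming on variables already derived, with no new data collection. The limitation is that the percentile measures exist only at height visits; the by-visit weight summaries cover the visits in between.
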